Categorical data will be summarized using descriptive statistics. The counts/proportions and 95% confidence interval will be reported. Continuous data will be summarized using descriptive statistics; mean, standard deviation, minimum, maximum, and median will be reported.

Descriptive summaries will be provided by treatment assignment (ixekizumab, adalimumab), JIA subtype (ERA, JPsA), bDMARD experience (bDMARD-naive or bDMARD-IR), and demographic features including sex and age group.

Pharmacokinetic data will be summarized using descriptive statistics.

An interim analysis will be performed to determine if the study should be stopped for futility when 40 ixekizumab-treated participants have completed 16 weeks of treatment. If the observed JIA ACR 30 response rate is less than 40% at interim, futility will be declared, and the study will be terminated after the applicable required regulatory agreements are obtained. All safety data will be descriptively summarized using corresponding populations.

Data Monitoring Committee:

Yes

2. Schedule of Activities

Table RHCG.2.1. Schedule of Activities – Open-Label Treatment Period

Visit No	Screening V1	Open-Label Treatment Period						Notes
		V2 Baseline	V3	V4	V5	V6	V7	
Study Week		W0	W2	W4	W8	W12	W16	
Study Days (Approximately)	-42 to -7d	0	14 ± 7d	28 ± 7d	56 ± 7d	84 ± 7d	112 ± 7d	
Informed consent and assent	X							Parent/legal guardian signs (informed consent form) and participant signs (assent form) (as appropriate) per local requirements. Signatures should be obtained before any study assessments, examinations, or procedures. If participant turns 18 during study, informed consent form is signed.
Complete medical history	X							Including TB exposure.
Review pre-existing conditions	X	X						
Immunization history record	X							Immunizations occurred prior to study entry.
Immunization record		X					X	Immunizations occurred during the participation in the study.
Demographics	X							Full date of birth (day, month, and year), sex, and ethnicity. In countries where full date of birth is not permitted to be collected, country-specific adjustments will be made to collect only month and year.
Physical examination	X						X	Excluding pelvic, rectal, and breast examinations.
Height	X	X				X		
Weight	X	X	X	X	X	X		Weight to be recorded to nearest 10th of a kilogram.
Occipital frontal circumference measurement		X				X		Only in children up to 3 years of age.

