6.1. Inclusion Criteria

Participants are eligible to be included in the study only if they meet all of the following criteria at enrollment:

Type of Participant and Disease Characteristics

- [1] Have a diagnosis with onset before the age of 16 years of any of the following categories of JIA as defined by the ILAR criteria (Petty et al. 2004):
 - ERA
 - JPsA
- [2] Have at least 3 active peripheral joints at screening and baseline. Active peripheral joint is defined as the presence of joint swelling or, in the absence of swelling, joint with limitation of motion plus pain on motion and/or tenderness on palpation.

Participant Characteristics

- [3] Participants with ERA must be from 6 to less than 18 years of age at screening and baseline.

Participants with JPsA must be from 2 to less than 18 years of age at screening and baseline.

Full date of birth will be collected except in countries in which it is not allowed.

- [4] Participants must weigh at least 10.0 kg.
- [5] Male or nonpregnant, non-breastfeeding female participants.

Participants of childbearing potential who are abstinent (if this is complete abstinence, as their preferred and usual lifestyle).

Total abstinence is defined as refraining from intercourse during the entirety of the study and for at least 12 weeks following the last dose of investigational product. Periodic abstinence such as calendar, ovulation, symptothermal, post ovulation methods, and withdrawal are not acceptable methods of contraception.

Otherwise, participants and their partners of childbearing potential must agree to use 2 effective methods of contraception, where at least 1 form is highly effective for the entirety of the study and for at least 12 weeks following the last dose of ixekizumab. Participants and their partners of childbearing potential must agree to use contraception for 5 months after the last dose of adalimumab.

The following contraception methods are considered acceptable (the participant, and their partner, should choose 2, and 1 must be highly effective [defined as less than 1% failure rate per year when used consistently and correctly]):

- Highly effective birth control methods:
 - Combined (estrogen- and progestogen containing) hormonal contraception associated with inhibition of ovulation: oral, intravaginal, or transdermal
 - Progestogen-only hormonal contraception associated with inhibition of ovulation: oral, intravaginal, or implantable

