5.1. Summary of Study Design

Study I1F-MC-RHCG (RHCG) is a multicentre, randomized, open-label study of subcutaneous (SC) ixekizumab, with adalimumab as a reference arm in children from 2 to less than 18 years of age, who are biologic disease-modifying antirheumatic drug- (bDMARD-) naive or inadequate responder (bDMARD-IR) as per investigator's judgement, with JIA subtypes of ERA (including juvenile-onset ankylosing spondylitis [JoAS]) and juvenile psoriatic arthritis (JPsA).

The study consists of 5 periods:

- **Screening Period** (Visit 1) will assess subject eligibility and will occur approximately 7 to 42 days before the Open-Label Treatment (OLT) Period (baseline; Week 0; Visit 2).
- **Open-Label Treatment Period** (OLT) will occur from Week 0 (baseline; Visit 2) to Week 16 (Visit 7). **CCI**
Evaluation of the primary endpoint will occur at Week 16.
- **Open-Label Extension Period** (OLE) will occur from Week 16 (Visit 7) to Week 104 (Visit 29/ Early Termination Visit [ETV]). All patients who were receiving ixekizumab in the OLT period will continue to receive ixekizumab for approximately 88 weeks during the OLE Period. Patients receiving adalimumab during the OLT period who did NOT attain a JIA ACR30 response at Week 16 will be switched to ixekizumab in the OLE period. Patients receiving adalimumab during the OLT period who did attain a JIA ACR30 response at Week 16 will be given the option to switch or not to switch to ixekizumab at any visit during the OLE period. The decision to switch for adalimumab-treated patients who achieved a JIA ACR30 response at Week 16 will be left to the patient/patient's caregiver and investigator. After switching to ixekizumab, the patients will not have the option to resume adalimumab treatment during the remainder of the trial participation.
- **Long-Term Extension Period** (LTE): Participants who complete the OLT and OLE periods will be participating in the LTE period of this study which will occur from Week 104 (Visit 29) to Week 264 (Visit 69/ ETV). All participants entering the LTE portion of the study period will receive weight-based ixekizumab at Week 104. Participants who were previously assigned to adalimumab will be switched to ixekizumab as described in Section 7.1 Treatments Administered of the protocol. If a participant previously assigned to adalimumab does not want to switch to ixekizumab in the LTE period of the study, the patient should initiate the ETV process at Week 104.

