6.12.5. Vital Signs and Other Physical Findings

Vital Signs evaluations will be summarized and analyzed for the following periods:

- OLT Period (Safety Population)
- OLE Period (OLE Period Population and OLE Switcher Population), and
- LTE Period (LTE Safety Population).

A listing of vital signs and other physical characteristics will be provided.

The planned summaries for vital signs (systolic blood pressure [BP], diastolic BP, pulse, weight, body mass index [BMI], temperature) are provided in [Table RHCG.6.13](#) and are described more fully in compound-level safety standards and in the vitals-related Pharmaceutical Users Software Exchange (PhUSE) white papers (Analyses and Displays Associated with Measures of Central Tendency – Focus on Vital Sign, Electrocardiogram, and Laboratory Analyte Measurements in Phase 2-4 Clinical Trials and Integrated Submission Documents [PhUSE 2013] and Analyses and Displays Associated with Outliers or Shifts from Normal to Abnormal: Focus on Vital Signs, Electrocardiogram, and Laboratory Analyte Measurements in Phase 2-4 Clinical Trials and Integrated Summary Documents [PhUSE 2015]).

Table RHCG.6.13. Summary Tables/Figures Related to Vital Signs

Analysis
Box plot for observed (spotfire)
Box plot for change from baseline (spotfire)
Tables with percentages of patients who shift from normal/high to low (i.e., treatment-emergent low) and percentages of patients who shift from normal/low to high (i.e., treatment-emergent high). The limits are defined in the compound-level safety standards and are based on literature.

For vital signs and physical characteristics, original-scale data will be analyzed. Mean changes from baseline and as incidence of abnormal values will be summarized.

The number and percentage of patients with treatment-emergent high blood pressure and pulse at any time for the populations mentioned in this section will be summarized. For treatment-emergent high blood pressure:

- A treatment-emergent prehypertension is defined as a change from a value less than the low limit of prehypertension at all baseline visits to a value that is within the limits of prehypertension at any time postbaseline during the treatment period.
- A treatment-emergent stage 1 hypertension is defined as a change from a value less than the low limit of stage 1 hypertension at all baseline visits to a value that is within the limits of stage 1 hypertension at any time postbaseline during the treatment period.

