- A treatment-emergent stage 2 hypertension is defined as a change from a value less than the low limit of stage 2 hypertension at all baseline visits to a value that is greater than or equal to the limits of stage 2 hypertension at any time postbaseline during the treatment period.

For treatment-emergent high or low value in pulse rate:

- A treatment-emergent high value is defined as a change from a value less than or equal to the high limit at all baseline visits to a value greater than the high limit at any time postbaseline during the treatment period.
- Treatment-emergent low value is defined as a change from a value greater than or equal to the low limit at all baseline visits to a value less than the low limit at any time postbaseline during the treatment period.

[Table RHCG.6.14](#) provides the blood pressure levels for children by age and gender and [Table RHCG.6.15](#) provides the criteria for abnormal treatment-emergent pulse rate in children and adolescents by age and gender.

Table RHCG.6.14. Blood Pressure Levels for Children by Age and Gender (Median Height)

Age (Year)	Hypertension Stage	Boy		Girl	
		Systolic BP (mmHg) (supine or sitting – forearm at heart level)	Diastolic BP (mmHg) (supine or sitting – forearm at heart level)	Systolic BP (mmHg) (supine or sitting – forearm at heart level)	Diastolic BP (mmHg) (supine or sitting – forearm at heart level)
6	Prehypertension	≥110 and <114	≥70 and <74	≥108 and <111	≥70 and <74
	Stage 1	≥114 and <126	≥74 and <87	≥111 and <124	≥74 and <86
	Stage 2	≥126	≥87	≥124	≥86
7	Prehypertension	≥111 and <115	≥72 and <76	≥109 and <113	≥71 and <75
	Stage 1	≥115 and <127	≥76 and <89	≥113 and <125	≥75 and <87
	Stage 2	≥127	≥89	≥125	≥87
8	Prehypertension	≥112 and <116	≥73 and <78	≥111 and <115	≥72 and <76
	Stage 1	≥116 and <128	≥78 and <91	≥115 and <127	≥76 and <88
	Stage 2	≥128	≥91	≥127	≥88
9	Prehypertension	≥114 and <118	≥75 and <79	≥113 and <117	≥73 and <77
	Stage 1	≥118 and <130	≥79 and <92	≥117 and <129	≥77 and <89
	Stage 2	≥130	≥92	≥129	≥89
10	Prehypertension	≥115 and <119	≥75 and <80	≥115 and <119	≥74 and <78
	Stage 1	≥119 and <132	≥80 and <93	≥119 and <131	≥78 and <91
	Stage 2	≥132	≥93	≥131	≥91
11	Prehypertension	≥117 and <121	≥76 and <80	≥117 and <121	≥75 and <79
	Stage 1	≥121 and <134	≥80 and <93	≥121 and <133	≥79 and <92
	Stage 2	≥134	≥93	≥133	≥92
12	Prehypertension	≥120 and <123	≥76 and <81	≥119 and <123	≥76 and <80
	Stage 1	≥123 and <136	≥81 and <94	≥123 and <135	≥80 and <93

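### The SAP's blood pressure and pulse limits run from age 6 to 17 only, so values at ages 2-5, and at 18 and over if age at visit is used, cannot be classified

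*SAP*

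**What the plan says.** SAP Section 6.12.5 plans to summarise "The number and percentage of patients with treatment-emergent high blood pressure and pulse at any time for the populations mentioned in this section". Those populations are the OLT safety, OLE, OLE switcher and LTE safety populations. None is defined by age (SAP Table RHCG.6.1).

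The section points to two tables for the limits. Table RHCG.6.14 "provides the blood pressure levels for children by age and gender", in single-year rows from 6 to 17. Table RHCG.6.15 gives pulse limits in four bands: 6-9, 10-11, 12-14 and 15-17. An event is treatment-emergent when the values at every baseline visit lie on the normal side of the limit and any later value in the period crosses it.

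The enrolled ages are wider than the tables. Protocol Section 6.1 states: "Participants with JPsA must be from 2 to less than 18 years of age at screening and baseline". The corresponding line for the other subtype is: "Participants with ERA must be from 6 to less than 18 years of age at screening and baseline". The gap at the lower end therefore concerns JPsA only. At the upper end, the note on consent in the Schedule of Activities (Protocol Section 2, Table RHCG.2.1) foresees participants reaching adulthood: "If participant turns 18 during study, informed consent form is signed". SAP Section 5.1 has the LTE running from Week 104 to Week 264.

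**The concern.** A threshold analysis needs a threshold for every value it is applied to. Here a blood pressure taken at age 4, or at age 18 if age at visit is used, has no printed row to be compared with. The SAP does not say whether such a value is missing, normal, or judged against the nearest row. If a program simply looks for values above a limit, a participant with no limit will appear as not abnormal.

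These counts have a use. Vital signs form part of a named secondary endpoint for the LTE (SAP Section 4.2), and treatment-emergent high and low vital signs go to the DMC as counts and percentages (SAP Section 6.15.1). The LTE is also where most participants who turn 18 will do so.

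**Working it through.** The plan gives no figure of its own to reproduce. The check compares the age rows with the eligibility ages and the length of each period.

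**Inputs.** Entry ages: 2 to under 18 for JPsA and 6 to under 18 for ERA (Protocol 6.1). Period ends: Weeks 16, 104 and 264 (SAP 5.1). Table ages: 6 to 17 (SAP 6.12.5). LTE safety baseline: Visit 1 to the first LTE injection (SAP 6.1.2.3).

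**Step 1: age reached at each milestone.** Years = weeks x 7 / 365.25.

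| Week | Years | Aged 18 by then if entry age is at least | Age of a child who entered at 2.0 |
|---|---|---|---|
| 16 | 0.307 | 17.69 | 2.31 |
| 104 | 1.993 | 16.01 | 3.99 |
| 264 | 5.060 | 12.94 | 7.06 |

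**Step 2: upper end, by age at visit.** A participant aged about 16.0 or over at entry is already 18 when the LTE begins, so no post-baseline LTE value has a row. The share of entrants affected is the 1.993-year width divided by the assumed age range:
- uniform over 6 to under 18: 1.993 / 12 = 16.6%, about 17%
- uniform over 10 to under 18: 1.993 / 8 = 24.9%, about 25%

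**Step 3: lower end.** A child who enters at exactly 2 reaches 6 at 4 x 365.25 / 7 = 208.7 weeks, so every entrant still on study is inside the table range by Week 264. That does not rescue the classification. In the OLT and LTE the baseline period reaches back to Visit 1, and treatment-emergence requires a value within limits at all baseline visits. A child enrolled at 2-5 has baseline visits with no row, so the condition stays undefined after the sixth birthday. The OLE safety baseline is a single value, usually at Week 16. Only children aged about 6 - 0.307 = 5.69 or over at entry would have a row by then.

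**Step 4: effect on a percentage.** If a share f of the denominator cannot be classified and is counted as normal, and the true rate is the same in everyone, then reported rate = true rate x (1 - f). With an assumed true rate of 10%:
- f = 17%: 10% x 0.83 = 8.3%
- f = 25%: 10% x 0.75 = 7.5%

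**Step 5: would age at consent solve it?** It is the only participant age that the SAP derives (Table RHCG.6.2, footnote a). It would keep nearly everyone below the upper end, but it leaves entrants aged 2-5 without limits throughout. It also judges growing children by old rows. A boy aged 12 at consent is 17 at Week 264 (12 + 5.06), yet would still be held to Stage 1 systolic pressure from 123 mmHg instead of 136, and to high pulse above 120 instead of above 100.

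**The case against.** The case on the other side has several sound parts.

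- **Turning 18 is not total exclusion.** One abnormal post-baseline value in the period is enough, so a participant can be counted at any in-range visit before the birthday. A reader might infer that everyone who turns 18 drops out of the count, and quote 5.06 / 12 = 42% or 5.06 / 8 = 63%. Those are the shares who turn 18 by Week 264. The shares with no in-range LTE visit are the 17% and 25% above, under the same assumptions.
- **Age at visit is not stated.** If age at consent applies, the upper gap all but disappears. This stands, and is why the upper-end figures are conditional. It does not help ages 2-5, and it brings the misclassification in Step 5.
- **The denominator is an inference.** SAP Section 6.12.5 does not state one, and Section 6.1 also reports how many participants provide data at each time point. If values without a limit were treated as missing, understatement would not follow. On the other side, the populations carry no age restriction, and the only denominator restriction in the general rules is for gender-specific events.
- **Other sources may hold limits.** Table RHCG.6.13 refers to compound-level safety standards, and Table RHCG.6.15 cites a separate guidance document. Neither is reproduced. A reader might infer that no limits exist anywhere for the missing ages, but the documents do not show that. They show only that the two tables named as supplying the limits lack them.
- **The consequence is bounded.** The summaries are descriptive. Listings, box plots and mean changes include all ages, and clinically significant findings are reported as adverse events at any age.

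**Conclusion.** The concern holds in this form. The printed limits do not fit the enrolled population, and no rule in the documents fills the gap. Values at ages 2-5 cannot be classified whichever age is used. Values at 18 and over cannot be classified if age at visit is used.

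The size is uncertain. At the upper end, about 17% to 25% of entrants would have no classifiable LTE visit, assuming age at visit, uniform entry ages and dropout unrelated to age. At the lower end no share can be computed, because the documents give neither the JPsA proportion nor its age distribution. Protocol Section 3.2 does describe an early JPsA peak at 2 to 4 years. Understatement follows only if unclassifiable participants remain in the denominator, which is the natural reading but is not written.

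This should be corrected before the safety summaries are programmed. It does not threaten the primary endpoint or any efficacy conclusion. The SAP already accepts the principle in Section 6.12.4, where it resets haematology limits because some age and sex reference ranges made a shift to Grade 1 impossible.

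**What to change.** Amend SAP Section 6.12.5 as follows.

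1. Add rows to Tables RHCG.6.14 and 6.15 for ages 2-5 and for 18 and over, or cite the specific reference source that supplies them. If the compound-level standards already cover these ages, a precise citation is enough.
2. State that age at each visit, baseline visits included, selects the limit.
3. Define the denominator at patient level as participants with an applicable limit at baseline and at least one post-baseline visit in the period. Report the number who cannot be classified beside each percentage. Counting participant-visits instead would not suit a summary that reports the percentage of patients.

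The cost is a few reference rows, minor programming and, where gaps remain, a slightly smaller denominator. No new data collection is needed.

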6.12.6. Growth Monitoring

Weight, height, and BMI data will be merged to the Centers for Disease Control and Prevention (CDC) standard growth data (released in 2000) by age and gender in order to compare patients' growth with the standard. Z-score and standardized percentile of weight, height, and BMI at each visit will be calculated and compared to the 2000 CDC growth charts (CDC 2023).

The z-score and percentile calculations are based on algorithms and data provided by the National Center for Health Statistics. The details are provided in the CDC website (<https://www.cdc.gov/nccdphp/dnpao/growthcharts/resources/sas.htm> [CDC 2019]).

- The following summaries will be provided in each treatment period with the corresponding safety population: baseline, mean change of actual measure, z-score and standardized percentile of weight, height, and BMI will be summarized.
- Patients' mean weight, height, and BMI standardized percentile will be plotted versus investigational product exposure time.

Height and weight will be measured at baseline and postbaseline for the assessment of physical growth according to the Schedule of Activities in the protocol. Occipital frontal circumference will be collected in patients up to 3 years of age. Height, weight and occipital frontal circumference changes in pediatric patients (both at an individual and group level) will be reviewed by the data monitoring committee (DMC).

6.12.7. *Children's Depression Inventory – 2*

The CDI-2 is a comprehensive multi-rater assessment of depressive symptoms in youth aged 7 to 17 years. When results from the CDI-2 are combined with other sources of verified information, the CDI-2 can aid in the early identification of depressive symptoms, the diagnosis of depression and related disorders, as well as the monitoring of treatment effectiveness (Kovacs 2010).

The CDI-2 quantifies depressive symptomatology using reports from children/adolescents (full-length and short), teachers, and parents (or alternative caregivers). It can be administered and scored using paper-and-pencil format with Multi-Health System's (MHS) QuikScore™ forms, or online through the MHS Online Assessment Center.

The CDI-2: Self-Report Short version (CDI-2:SR[S]) is an efficient screening measure that contains 12 items and takes about half the time as the full-length to administer (5–10 minutes).

Scoring the CDI-2:SR(S): Each of the 12 items is scored from 0-2.

A change from baseline summary analysis will be presented for the Safety Population, the OLE Period Population, and the LTE Safety Population. A shift table will be produced showing the number and percentage of patients shifting from baseline score to a maximum postbaseline score in categories of <6 and ≥6 for the Safety Population, the OLE Period Population, and the LTE Safety Population.

6.12.8. *Columbia-Suicide Severity Rating Scale (C-SSRS)*

The C-SSRS is an assessment tool that evaluates suicidal ideation and behavior. Information on the C-SSRS scale can be found through the following link: http://cssrs.columbia.edu/wp-content/uploads/C-SSRS_Pediatric-SLC_11.14.16.pdf (RFMH 2008).

Specifically, the following outcomes are C-SSRS categories and have binary responses (yes/no). The categories have been re-ordered from the actual scale to facilitate the definitions of the composite and comparative endpoints, and to enable clarity in the presentation of the results.

Category 1 – Wish to be Dead

Category 2 – Non-specific Active Suicidal Thoughts

Category 3 – Active Suicidal Ideation with Any Methods (Not Plan) without Intent to Act

Category 4 – Active Suicidal Ideation with Some Intent to Act, without Specific Plan

Category 5 – Active Suicidal Ideation with Specific Plan and Intent

Category 6 – Preparatory Acts or Behavior

Category 7 – Aborted Attempt

Category 8 – Interrupted Attempt

Category 9 – Actual Attempt (non-fatal)

Category 10 – Completed Suicide

Self-injurious behavior without suicidal intent is also a C-SSRS outcome (although not suicide-related) and has a binary response (yes/no).

Composite endpoints based on the above categories are defined below.

- **Suicidal ideation:** A “yes” answer at any time during treatment to any 1 of the 5 suicidal ideation questions (Categories 1-5) on the C-SSRS.
- **Suicidal behavior:** A “yes” answer at any time during treatment to any 1 of the 5 suicidal behavior questions (Categories 6-10) on the C-SSRS.
- **Suicidal ideation or behavior:** A “yes” answer at any time during treatment to any 1 of the 10 suicidal ideation and behavior questions (Categories 1-10) on the C-SSRS.

The Self-Harm Supplement Form is a 1-question form that is completed, at any visit, including baseline visit, that asks for the number of suicidal behaviors, possible suicidal behaviors, or nonsuicidal self-injurious behaviors the patient has experienced since the last assessment. For each unique event identified, a questionnaire (Self-Harm Follow-up Form) which collects supplemental information on the self-injurious behavior is to be completed.

Given that few or no suicidal ideation or behaviors are anticipated, C-SSRS will be listed by patient and visit. Only patients that show suicidal ideation/behavior or self-injurious behavior without suicidal intent will be displayed (that is, if a patient’s answers are all “no” for the C-SSRS, then that patient will not be displayed). However, if a patient reported any suicidal ideation/ behavior or self-injurious behavior without suicidal intent at any time point, then all his/her ideation and behavior will be displayed, even if not positive. Note that missing data should not be imputed.

The Self-Harm data will be listed by patient and visit if number of events on Self-Harm Supplement Form is not zero in the eCRF Self Harm Questionnaire Supplement.

